In Phase II (Years 02-05), we will test our intervention using a two-arm cluster randomized control trial in 30 rural primary care clinics using program training and practice facilitation to support implementation. Participating clinics will be randomized into two groups: Intervention and Usual Care. Randomization will be stratified on health system. As in the pilot, the intervention combines: (1) a clinic-health planvendor supported direct-mail fecal testing program with targeted outreach for patients who have never been screened or who have yet to establish care and (2) patient navigation for those who are referred for colonoscopy as either the primary screening or for follow-up from an abnormal fecal test. We will evaluate effectiveness, implementation, and maintenance of the intervention through quantitative and qualitative measures. Results from the trial will inform scale-up of the program through partnerships with 20 regional and national organizations that serve rural/frontier primary care clinics using webinars, train-the-trainer workshops and collaborative learning activities.

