#### 4.0 STUDY POPULATION

The study team will recruit eligible CCOs and rural clinics, and we will work in turn with clinics to engage providers, staff, and patients. Our eligibility criteria for CCOs, clinics, clinics staff, patients and organizational partners are below.

CCOs/CCO staff: 1) serving a majority of counties that are predominantly rural based on 2010 RUCA Codes (Codes 4-10); 2) willing to participate in data collection activities (e.g., producing claims data, interviews).

Clinics: 1) Clinics will be eligible for the cluster randomization if there are 30 or more patients eligible for screening, 2) are classified as rural according to RUCA (Codes 4-10) or Oregon Office of Rural Health designations, 3) are served by CCOs agreeing to participate in the project; and 4) willing to implement the intervention into their clinic for the study.

Clinic Staff/Providers: 1) employed as a clinician or ancillary staff member in a participating clinic; 2) willing to participate in data collection activities (e.g., interviews, observation, surveys).

Patients: 1) attributed to participating clinic; and 2) are enrolled in Medicaid or Dual eligible; 3) eligible for CRC screening;

a. For the subset of patients that will be invited to participate in key informant interviews, a 5th eligibility criteria is consent to participate.

Exclusion criteria: Clinics are excluded if they have current or ongoing participating in other mailed fecal testing research projects in the Medicaid population. Patients are excluded if they are current for screening, have comorbid conditions that make patients poor candidates for screening based on clinical judgment (e.g., end-stage renal disease, enrollment in hospice), are not an established patient or for other reasons documented by the clinics.

Community or regional/organizational partners (includes endoscopy providers, community-based outreach workers, or leaders from regional or national organizations who participate in the pilot, pragmatic trial, or scale-up study) 1) involved in study activities (training, care delivery); 2) willing to participate in data collection activities (e.g., trainings, interviews, surveys).

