Patient interviews: We will conduct one-on-one interviews with patients who receive the direct mail and patient navigation programs. Interviews will explore patient experiences with the program, including reaction, acceptability, satisfaction, and perceptions of usefulness; facilitators of, and barriers to, participating in the program and obtaining a follow-up colonoscopy; unintended consequences; and suggestions for improvement

Interviews and surveys with regional and organizational partners: To assess perceptions of the intervention and its impact on the broader community, we will interview CCO leaders, endoscopy providers (e.g., GI specialists, general surgeons, primary care clinicians) who treated study participants, and community organizations, including transportation service providers. Up to three interviews will occur throughout the duration of the study, including at baseline (pre-implementation), at the mid-point (approximately 12 months after the first-year implementation start), and post-implementation (approximately 12 months after the second-year implementation start). To evaluate the impact of scale-up activities we will conduct interviews and brief evaluation surveys with organizational leaders who participate in the trainings.

Patient outcomes data and patient navigation registry (Evaluation): Direct mail outreach and patient navigation activities will be tracked using reports from direct mail vendors, claims data from participating Medicaid health plans, clinic data from the electronic health record, chart abstraction data conducted by ORPRN or clinic staff, and data on navigation from a REDCap database. The mailed FIT and patient navigation interventions will be delivered by clinic and health plan staff as part of standard care. Clinics will be randomized to implement the interventions in different years to provide comparison groups. Claims data will be sent to the research team at OHSU from the participating payers based on their data pull of patients eligible for CRC screening in the clinics randomized to implement the intervention. Vendor reports will be sent to the CCO and research team based at OHSU. A clinic-level chart audit will be used to evaluate CRC screening and follow-up colonoscopy for patients with an abnormal FIT in intervention and control clinics.

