Data for this project (i.e., process and survey data elements and patient navigation outcomes (such as number of patients who received patient navigation, number of patients with missed / canceled appointments or inadequate bowel preparation), will be stored in OCTRI's installation of REDCap, a highly secure and robust web-based research data collection and management system.

Features of REDCap that protect participants' privacy and data security include:

[figure not shown]
• Physical Security: OCTRI's REDCap software is housed on servers located in ITG's Advanced Computing Center providing locked physical security

- Electronic Security: The REDCap servers are housed behind both the OHSU firewall and a second ACC firewall. All transmissions of data from the application are encrypted over HTTPS with the industry standard TLS 1.1 protocol (AES 256-bit encryption).
- Controlled User Access: REDCap employs a robust multi-level security system that enables researchers to easily implement "minimum necessary" data access for their research staff, including specification of data fields that are identifiers. This feature includes "single click" ability to provide completely deidentified (removing all identified data fields and shifting dates) for analysis or other purposes. User activities are logged to enable auditing of all data access. Access is integrated with OHSU's network such that users who are also OHSU employees are authenticated against their OHSU network credentials.
- Data Integrity: REDCap is jointly managed in accordance with OHSU Information Security Directives by ACC staff and members of OCTRI's Biomedical Informatics Program, ensuring fidelity of database configuration and back-ups. User activities are logged to enable auditing of all data changes.

Data from the vendor and REDCap database will be merged with claims data to generate evaluation reports. To avoid bias in colonoscopy capture across baseline and follow-up time-points, ORPRN practice facilitators will perform a chart audit on all patients who were eligible for the direct mail program. The chart audit will confirm FIT completion and monitor for colonoscopy referral and receipt, pathology results, and referral to care (i.e. surveillance or cancer treatment), as indicated.

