recruit clinics; conduct	exclusion criteria for CCOs and clinic	literature,	board on inclusion and exclusion	2020		
baseline assessment; use	participation in Phase II.	statistical power	criteria			
results from pilot to		requirements				
prepare to conduct a	b. Develop CCO and clinic	Relevant	Feedback from local advisory	Jan – Mar		
large-scale, pragmatic	recruitment materials	literature	board	2020		
implementation-	b. Successfully engage 3 CCOs and 30	Feasibility data	List of participating CCOs and	Mar – Sep		
effectiveness trial and	rural/frontier clinics for the main trial	from pilot study	selected clinic characteristics	2020		
scale-up (see Phase II).	d. Develop manual outlining trial	Feasibility data	Feedback from advisory board on	Apr – Sep		
	protocols (including quality assurance	from pilot study	recruitment materials; study	2020		
	protocols), scopes of work, and		protocol; scope of work			
	associated budgets.					

Aims	Assessment/	Data Sources	Description	Timeline
	Measurement			
Aim 1. Conduct a large-scale pragmatic study, cluster randomized control trial, to assess the implementation, effectiveness, and maintenance of the program piloted in Phase I in 30 rural primary care clinics (n ~ 3,960 patients aged 45 – 75) using practice facilitation to support implementation. Using a mixed methods approach, identify patient-, clinic/health system-, and payer/policy/community-level factors that are associated with reach, effectiveness, implementation and maintenance	Assessment of effectiveness (patient and clinic level).	Administrative data, claims data, EHR data from clinics, vendor data, laboratory data, survey data.	Patient Level Outcome (Primary): Completion of any CRC screening Clinic Level Outcome: Proportion of Medicaid patients screened for CRC We will compare the intervention vs. control clinics after adjusting for baseline at 6 and 12 months. The primary endpoint is 6 months. Secondary outcomes: completion of testing types (fecal testing, FIT-DNA, CT Colonography, Colonoscopy, Flex Sigmoidoscopy; patient level) and % completion (clinic level); time to screening from study-eligible patient list pull (patient level); FIT results (patient level); follow-up colonoscopy completion (patient level); time to colonoscopy from abnormal FIT result (patient level); and adenomas or cancers detected (patient level).	2021-Sep 2024

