The primary effectiveness outcome of this study at the patient level is the completion of any colorectal cancer (CRC) screening (for study-eligible patients). Consistent with the pragmatic nature of the trial, we will use claims, vendor data, and EHR data for calculating CRC screening outcomes. Comparing the likelihood of receiving CRC screening between intervention and usual care groups at 6-month post participant list-pull date, we hypothesize that CRC screening will be more likely in patients allocated to the intervention group versus the usual care group. To examine the effectiveness of the program CRC screening completion at 6 months, we will use the generalized form of the hierarchical linear model (HLM; using a logit link and binomial distribution, aka multilevel logistic regression) to account for the clustering of patients within clinics and the assignment to arm at the clinic level. The variables that will be included in the model are the clinic baseline screening rate (if available) and a binary indicator of arm (1=tailored, 0=standard) as fixed effects and clinic is a random effect. A positive and significant coefficient for arm would provide support for the effectiveness of the intervention. We will do a moderator analysis at all levels to explore the impact of patient and clinics characteristics (see outcomes table above), and implementation components affecting outreach on completion likelihood in groups of patients determined at analysis (e.g. never screened, Hispanic, etc.).

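### Follow-up colonoscopy and time to colonoscopy can be read as arm comparisons among abnormal-FIT patients, a group formed after randomization, and should be labelled descriptive

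*Combined protocol and SAP*

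**What the plan says.** Section 1.0 describes one randomized package with two parts. The first is a "direct-mail fecal testing program with targeted outreach for patients who have never been screened or who have yet to establish care". The second is "patient navigation for those who are referred for colonoscopy as either the primary screening or for follow-up from an abnormal fecal test". Clinics are randomized to this package or to usual care.

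Section 7.0 (patient outcomes data) says a clinic-level chart audit will be used to evaluate CRC screening and "follow-up colonoscopy for patients with an abnormal FIT in intervention and control clinics".

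In Section 8.0, the Phase II Aim 1 row on assessment of effectiveness states: "We will compare the intervention vs. control clinics after adjusting for baseline at 6 and 12 months". The same cell then gives the secondary outcomes, among them "follow-up colonoscopy completion (patient level); time to colonoscopy from abnormal FIT result (patient level").

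Section 9.0 defines the primary outcome as "completion of any colorectal cancer (CRC) screening (for study-eligible patients") and specifies a multilevel logistic model for it at 6 months. It states intention-to-treat for the primary analysis. It gives no model for any secondary outcome. Nowhere are the two colonoscopy outcomes called descriptive or exploratory.

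**The concern.** Only a patient who completes a FIT can have an abnormal one, and the intervention mails FITs. The denominator for both colonoscopy outcomes is therefore shaped by part of the treatment being tested. Outreach is aimed partly at never-screened patients, so the abnormal-FIT group in intervention clinics may differ in make-up from the one in usual-care clinics. Randomization does not protect a comparison between those groups, and adjusting for a clinic's baseline screening rate does not restore the protection.

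These are the two listed secondary outcomes on follow-up after an abnormal FIT, the step that navigation is meant to improve. Without a label, a difference by arm could be credited to navigation, or held against it, when it partly reflects who returned a kit.

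**Working it through.** **1. The group.** Time to colonoscopy starts at the abnormal result, so it is conditional on that result by definition. Section 7.0 applies the same condition to follow-up colonoscopy, in both arms. The condition is met after clinics are randomized.

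**2. Inputs.** The documents give about 3,960 patients (Section 8.0), or 1,980 per arm if the arms are equal, which is an assumption. They give no rate for FIT completion, abnormal results or follow-up colonoscopy, so there is no stated figure to reproduce and every rate below is assumed:
- FIT completion: c0 = 8% in usual care and c1 = 20% in intervention (wider: 5-10% versus 15-25%).
- Abnormal results: a = 8% of completers (wider: 5-10%), the same for both kinds of completer.
- Follow-up colonoscopy: f = 65% in patients who would complete a FIT under usual care, and m in the extra, mail-prompted completers, with m − f between −30 and +30 points.
- Patients who complete under usual care would also complete under the intervention.

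**3. Selection with no navigation effect.** Follow-up in the intervention arm is [c0·f + (c1 − c0)·m]/c1, so the arm difference is (1 − c0/c1)(m − f).
- Central: (1 − 0.08/0.20) × 0.30 = 0.18, so 0 to 18 points, with the sign of the gap.
- Widest: (1 − 0.05/0.25) × 0.30 = 0.24.
- If m = f, the difference is zero.

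A second illustration let one latent adherence trait drive both FIT completion and colonoscopy (log-odds slope 0.5 to 1.5, completion 5-10% versus 10-20%). It gave −0.3 to −7.7 points with no true arm effect.

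**4. Precision.**
- Abnormal FITs: 1,980 × 0.08 × 0.08 = 12.7 versus 1,980 × 0.20 × 0.08 = 31.7.
- Half-width at 65% versus 53% (a gap of −20 points): 1.96 × √(0.65 × 0.35/12.7 + 0.53 × 0.47/31.7) = 0.315.
- Over gaps of −30 to +30 points: 0.293 to 0.315. Over the wider inputs: 0.235 to 0.491.
- With the 4,500 patients in Section 1.0: 14.4 versus 36.0 abnormal FITs, half-width 0.295.

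These figures ignore clustering, and the normal approximation is rough at such counts.

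**5. An outcome on all eligible patients.** Take abnormal FIT followed by colonoscopy, yes or no, in everyone, again with no navigation effect.
- Usual care: 0.08 × 0.08 × 0.65 = 0.00416, or 8.2 events.
- Intervention: 0.08 × (0.08 × 0.65 + 0.12 × m) = 0.00752, 0.0104 and 0.01328 at m = 0.35, 0.65 and 0.95, or 14.9, 20.6 and 26.3 events.
- Half-width: 4.7 to 5.8 per 1,000 before clustering.
- Total events over the wider inputs, 1,980 × a × [2·c0·0.65 + (c1 − c0)·m]: from 1,980 × 0.05 × (0.065 + 0.10 × 0.35) = 9.9 to 1,980 × 0.10 × (0.13 + 0.15 × 0.95) = 54.0.

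Events rise from 8.2 to 20.6 at m = f, through FIT uptake alone.

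**6. Window.** Section 7.0 has clinics implementing in different years. Section 8.0 puts first-year implementation in 2021 and second-year implementation in Spring 2022. If usual-care clinics start in Spring 2022, a 12-month window from any list pull after spring 2021 would run past that start.

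**The case against.** The strongest reply is that the arm comparison is inferred. In the Section 8.0 cell, the comparison sentence follows the primary outcomes and comes before the secondary list. Its baseline adjustment suits a screening rate and has no stated counterpart for time from an abnormal result. The Section 7.0 sentence describes what a data source is for. Section 9.0 states one hypothesis, on screening. All of this stands. A reader might infer that the plan commits to testing navigation by comparing arms among abnormal-FIT patients; no passage says so. What remains is that both outcomes sit under assessment of effectiveness, Section 7.0 names both arms, and nothing rules out a causal reading when results are reported.

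A second reply is that imprecision limits the harm. On the central inputs, selection alone would give a nominally significant difference about 5-7% of the time at gaps of 0-10 points, and 20-23% at 30 points. For example, a difference of −0.18 with standard error 0.315/1.96 = 0.161 gives about 20%. This also stands, and it keeps the point modest.

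A third reply is that the larger gap is the absence of any written secondary analysis. That is fair, but writing a by-arm model for these two outcomes would not cure the selection.

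**Conclusion.** The point holds as a matter of design: read together, Sections 7.0 and 8.0 allow an arm comparison in a group formed after randomization, and such a difference would not isolate navigation.

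Three stronger inferences are not supported:
- **That the bias is large, or runs in a known direction.** Both illustrations rest on assumed rates, they disagree on size, and zero is possible.
- **That outreach to patients without established care drives the selection.** Section 1.0 targets them, but Section 4.0 excludes patients who "are not an established patient or for other reasons documented by the clinics", so only the never-screened targeting is relied on here.
- **That the main result is compromised.** The primary outcome is defined on study-eligible patients and is unaffected.

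The comparison would also be too imprecise, on these assumptions, to support a firm conclusion often. This is a cheap improvement worth making.

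**What to change.** **Minimum change.** In Section 9.0 and the Section 8.0 outcomes table, state that colonoscopy completion and time to colonoscopy among abnormal-FIT patients are reported descriptively by arm, with numbers of patients and intervals and no causal claim about navigation. The cost is a few sentences.

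**Optional, if between-arm inference on follow-up is wanted.** Define the outcome as abnormal FIT followed by colonoscopy, among all study-eligible patients, within a fixed window from list pull. Analyse it with clustering by clinic, and interpret it as an effect of the combined program. The primary multilevel model would serve. If events are too sparse for it, use a pre-stated permutation test on clinic proportions, stratified by health system. The window must close before any usual-care clinic starts the program. Twelve months may fail this for later list pulls, so check the actual dates before choosing.

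No new data collection is needed: Section 7.0 plans the audit in both arms and says "ORPRN practice facilitators will perform a chart audit on all patients who were eligible for the direct mail program", and Section 10.2 also covers all patients eligible for screening. The drawbacks are that this outcome is sparse, that it rises with FIT uptake even if navigation does nothing, and that a short window gives late FIT completers less time for colonoscopy. No outcome in this two-arm design isolates navigation.

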# SCHEDULE OF EVENTS

# 8.0 TIMELINE AND MILESTONES

Phase I practice and CCO participants will be recruited Fall 2019, with the pilot intervention complete by the end of year 1. Phase II practice and CCO participants will be recruited in Fall/Winter 2020-2021 and first year of implementation will occur in 2021, with second-year implementation occurring in Spring 2022.

Phase I Milestones and Timeline						
Aim	Milestones	Information sources	Measurement / Validation	Timeline		
1. Adapt direct mail materials and outreach to hard-to engage rural patients	a. Identify and recruit rural Medicaid patients to participate in Boot Camp Translation.	ORPRN, CHARA, CCOs, primary care clinics	Number approached and engaged. Demographic and geographic characteristics	Oct 2019 – Dec 2019		
	b. Host Boot Camp Translation sessions; adapt program and identify outreach for patients at risk (unestablished, never screened).	Boot Camp Translation, relevant literature	Session attendance, evaluations, modifications of program messaging, timing, materials	Jan – May 2020		
2. Conduct pilot to test the feasibility, effectiveness and acceptance of patient navigation program.	a. Update registry tools (tools will track total FIT kit mailings, test results, receipt of follow-up care, and display patient's previous CRC screening history). Implement patient navigation pilot.	Claims, vendor/lab data, EHR data Navigation registry	Registry; vendor to identify patients needing follow-up; tools for tracking navigated patients and CRC-related outcomes in EHR or registry.	Oct 2019 – Apr 2020		
	b. Obtain data on patients participating in direct mail program and FIT results; Assess the pilot intervention's preliminary reach and effectiveness based on receipt of direct mail, FIT or colonoscopy completion, and proportion of patients receiving navigation.	Claims, vendor/lab data, EHR data	N FITs completed / FITs mailed; across stratification variables.  N patients with abnormal FITs; documented receipt of navigation and outcome.	Apr – Jul 2020		
	c. Assess the interventions feasibility and acceptance, based on one-on-one interviews with patients and debrief interviews with clinic/CCO staff.	Relevant literature	Feedback from patients and providers.	Apr – Jul 2020		

Phase I Milestones and Timeline						
Aim Milestones		Information	Measurement / Validation	Timeline		
		sources				
3. Engage CCOs and	a. Creation of a list of inclusion and	Relevant	Feedback from local advisory	Jan – Mar		
recruit clinics; conduct	exclusion criteria for CCOs and clinic	literature,	board on inclusion and exclusion	2020		
baseline assessment; use	participation in Phase II.	statistical power	criteria			
results from pilot to		requirements				
prepare to conduct a	b. Develop CCO and clinic	Relevant	Feedback from local advisory	Jan – Mar		
large-scale, pragmatic	recruitment materials	literature	board	2020		
implementation-	b. Successfully engage 3 CCOs and 30	Feasibility data	List of participating CCOs and	Mar – Sep		
effectiveness trial and	rural/frontier clinics for the main trial	from pilot study	selected clinic characteristics	2020		
scale-up (see Phase II).	d. Develop manual outlining trial	Feasibility data	Feedback from advisory board on	Apr – Sep		
	protocols (including quality assurance	from pilot study	recruitment materials; study	2020		
	protocols), scopes of work, and		protocol; scope of work			
	associated budgets.					

Aims	Assessment/	Data Sources	Description	Timeline
	Measurement			
Aim 1. Conduct a large-scale pragmatic study, cluster randomized control trial, to assess the implementation, effectiveness, and maintenance of the program piloted in Phase I in 30 rural primary care clinics (n ~ 3,960 patients aged 45 – 75) using practice facilitation to support implementation. Using a mixed methods approach, identify patient-, clinic/health system-, and payer/policy/community-level factors that are associated with reach, effectiveness, implementation and maintenance	Assessment of effectiveness (patient and clinic level).	Administrative data, claims data, EHR data from clinics, vendor data, laboratory data, survey data.	Patient Level Outcome (Primary): Completion of any CRC screening Clinic Level Outcome: Proportion of Medicaid patients screened for CRC We will compare the intervention vs. control clinics after adjusting for baseline at 6 and 12 months. The primary endpoint is 6 months. Secondary outcomes: completion of testing types (fecal testing, FIT-DNA, CT Colonography, Colonoscopy, Flex Sigmoidoscopy; patient level) and % completion (clinic level); time to screening from study-eligible patient list pull (patient level); FIT results (patient level); follow-up colonoscopy completion (patient level); time to colonoscopy from abnormal FIT result (patient level); and adenomas or cancers detected (patient level).	2021-Sep 2024
and to assess program adaptations.	Assessment of implementation (compliance rate with program components at clinic level).	Administrative data, claims data, vendor data, laboratory data, survey data including debriefs.	Proportion of core activities performed (e.g., mailed FITs, patient navigation calls) by clinics/CCOs	2021-2024
	Assessment of maintenance (compliance rate with program over time at clinic level).	Administrative data, claims data, vendor data, laboratory data, survey data.	Proportion of intervention clinics sustaining program in second year (N core activities sustained in second year/ N core activities, in intervention clinics/CCOs). Effectiveness of the program in intervention clinics in Year 2.	2021-2024
	Assessment of maintenance (compliance rate with program at patient level)		Proportion of patients who completed FIT in Year 1 who complete in Year 2, in intervention clinics.	

	Assessment of program second year implementation and adaptations.	Clinic/CCO surveys and interviews.	Types of and reasons for program adaptations, based on Wiltsey-Stirman FRAME framework.	May 2023- Sep 2024
Aim 2. Partner with regional and national organizations ( $n\sim20$ ) to scale-up the program to additional clinics serving rural and underserved patients in high priority geographic regions of the US ( $n\sim130$ clinics; 17,000+ patients) using webinars, trainthe-trainer workshops and collaborative learning approaches. Assess trainings delivered, program adoption and adaptations and determinants of dissemination success.	a. Assessment of adoption by clinics and community organizations.	Participation in workshops, training, and collaborative learning activities; survey data; use of	N clinics, community organizations, and staff that participate in training workshops, train-the-trainer sessions, and collaborative learning activities.  Adoption as reported on 6-month survey data of workshop participants.	2021-2024
		program tools and implementation materials.	Use of program tools; downloads of training and implementation materials.	
	b. Assessment of program adaptations.	Clinic and community organization surveys and interviews.	Types of and reasons for program adaptations.	Oct 2023- Sep 2024

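### The patient-level maintenance measure keeps first-year FIT completers who are no longer eligible for a FIT in its denominator, so it falls as colonoscopy navigation succeeds

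*Combined protocol and SAP*

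**What the plan says.** In the combined protocol and SAP, the Phase II table of section 8.0 has one row labelled as maintenance at patient level: "Assessment of maintenance (compliance rate with program at patient level". Its definition is "Proportion of patients who completed FIT in Year 1 who complete in Year 2, in intervention clinics". No limit is set on the FIT result, on later colonoscopy, or on eligibility in the second year. Section 9.0 does not mention the measure.

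Three other parts of the plan bear on who can contribute a second FIT:

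- The abstract (section 1.0) describes the second intervention component as "patient navigation for those who are referred for colonoscopy as either the primary screening or for follow-up from an abnormal fecal test".
- The Aim 1 effectiveness row in section 8.0 lists "follow-up colonoscopy completion (patient level" among the secondary outcomes, so that colonoscopy is a result the program seeks.
- Section 4.0 states: "Patients are excluded if they are current for screening". It also requires that patients be "attributed to participating clinic" and that they "are enrolled in Medicaid or Dual eligible".

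On timing, section 8.0 says only that "first year of implementation will occur in 2021, with second-year implementation occurring in Spring 2022".

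**The concern.** The row is meant to measure compliance with the program. A patient to whom the program does not offer a second FIT can neither comply nor fail to comply, yet the stated denominator scores that patient as a failure. The clearest case is an abnormal first-year FIT followed by a navigated colonoscopy: one row of the table counts this as success, and the maintenance row counts it as loss.

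The results are to inform scale-up. A low value on this measure could mean that patients disengaged, that they were successfully taken to colonoscopy, or that they were not yet due. As defined, the measure cannot tell these apart, and it moves in the wrong direction for the second.

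**Working it through.** The plan gives no target, expected value or sample size for this measure, so there is no figure to reproduce. The check is of direction first, then size.

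**Inputs.** From the documents: the denominator (section 8.0), the navigation path (section 1.0), follow-up colonoscopy as an outcome (section 8.0), and the exclusion of patients who are current (section 4.0). Not in the documents, and therefore assumed:

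- *a*, share of first-year FITs that are abnormal: 4-10%
- *c*, share of abnormal FITs followed by a completed colonoscopy: 40-80%
- *r*, second-year repeat rate among patients who are eligible to repeat: 50% for illustration (range 30-70%)

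**Formula.** Let *x* be the share of first-year completers not eligible to repeat, and suppose none of them does a FIT. Of *N* completers, *N*(1 − *x*) are eligible and *rN*(1 − *x*) repeat. The measure as written is *M* = *r*(1 − *x*); on an eligible denominator it is *r*. The relative understatement is (*r* − *M*)/*r* = *x*, whatever the value of *r*.

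**Direction.** Suppose only patients with a completed follow-up colonoscopy become ineligible, so *x* = *a* × *c*, and abnormal-FIT patients without colonoscopy repeat at rate *r*. With *a* = 10% and *r* = 50%:

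- *c* = 0: *M* = 0.50 × (1 − 0) = 50.0%
- *c* = 40%: *M* = 0.50 × (1 − 0.04) = 48.0%
- *c* = 80%: *M* = 0.50 × (1 − 0.08) = 46.0%

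Doubling colonoscopy completion from 40% to 80% lowers the score by 2 points, with no change in anyone's willingness to repeat a FIT.

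**Size.** At *r* = 50%:

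| *a* | *c* | *x* = *ac* | *M*, only completed colonoscopies ineligible | *M*, all abnormal FITs ineligible (*x* = *a*) |
|---|---|---|---|---|
| 4% | 40% | 1.6% | 49.2% | 48.0% |
| 7% | 60% | 4.2% | 47.9% | 46.5% |
| 10% | 80% | 8.0% | 46.0% | 45.0% |

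The relative understatement is 1.6-8.0% if only completed colonoscopies count as ineligible, and 4-10% if all abnormal FITs do: about 2-10% over both. At *a* = 10% and *c* = 80%, the absolute loss is 2.4, 4.0 and 5.6 points for *r* = 30%, 50% and 70%.

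**Patients with a first-year FIT that is still current.** They add to *x* in the same way, but the plan defines neither how long a FIT keeps a patient current nor when the second-year list is pulled. No value can be put on this part.

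**The case against.** Several stronger readings are tempting, and the case against them is good.

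- *Most first-year completers will still be current at the second round.* A reader might infer this from the dates 2021 and Spring 2022. If a FIT counted for 12 months, returns were spread evenly over April-December 2021, and a single list were pulled at the end of May 2022, then 7 of 9 months' completers (78%) would still be current. None of these conditions is in the documents. Section 9.0 also plans for as much as 18 months of data after each mailing. On the same 12-month assumption, every one of those tests would lapse by the end of December 2022, inside that period. The timing effect is possible but not established.
- *Patients who left Medicaid or the clinic are wrongly counted.* Adding an assumed 25% loss to 10% abnormal would give *x* = 1 − 0.90 × 0.75 = 32.5%. But retention among everyone reached in the first year is a legitimate quantity in a pragmatic trial, and conditioning on later enrolment selects on post-baseline status. This is a choice of estimand, not an error.
- *Every abnormal FIT bars a repeat.* The documents do not say that an abnormal FIT without colonoscopy makes a patient current.
- *A second-year screening colonoscopy counts as failure.* The definition does not say what must be completed in the second year. That is ambiguous rather than wrong. Reading it as any screening still gives no credit for a follow-up colonoscopy done in the first year.
- *Maintenance goes otherwise unmeasured.* The adjacent row also lists second-year effectiveness, and follow-up colonoscopy is already a secondary outcome.

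The measure is also descriptive, with no test, target or comparison between arms. All of this limits the size and consequence of the problem. None of it narrows the stated denominator or removes the wrong-direction effect.

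**Conclusion.** The point holds in a limited form. The denominator is all first-year FIT completers. Patients with a completed follow-up colonoscopy after an abnormal FIT, and others still current, remain in it and count against the program if they do no second-year FIT. The measure therefore falls as navigation succeeds. This takes a completed colonoscopy to make a patient current under section 4.0, which is the natural reading although the term is undefined.

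The relative understatement from the abnormal-FIT path is about 2-10%, resting wholly on the assumed rates above and on ineligible patients doing no FIT. That is modest. Any addition from the spacing of the rounds cannot be sized from the documents. The primary 6-month comparison is not affected.

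**What to change.** In the Aim 1 table of section 8.0:

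1. Define the main denominator as first-year FIT completers in intervention clinics who are again eligible, that is, not current for screening under section 4.0, during a stated second-year window. State for this purpose what current means and whether it covers an abnormal FIT without colonoscopy.
2. Report patients with an abnormal first-year FIT separately, by completion of follow-up colonoscopy.
3. State that completing in the second year means any CRC screening, with FIT shown separately.
4. Keep the all-completers proportion, including patients who left Medicaid or the clinic, as a supplementary figure.

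The FIT results, claims and chart audit already planned in section 7.0 supply what is needed. The cost is a smaller denominator, hence a less precise proportion, and slightly more analysis.
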